4.2. Description of type/design of the trial/randomization/intended purpose of the VR technology

PurePurr-001 is a randomized, prospective, sham-controlled, blinded, cross-over clinical study. The study will include healthy volunteers aged 20 to 60 years, who have applied to the study site for other medical reasons or those who read the advertisement on the Internet. After signing the Informed Consent Form for participation in the clinical study, an assessment of healthy volunteers’ eligibility with the inclusion/non-inclusion criteria will be carried out.

Study groups

Eligible volunteers will be randomized at the 1:1 ratio to one of the following study groups (1 or 2):

Group 1: the volunteers will first be tested with the VR headset A, and during the next visit – with the VR headset B.

Group 2: the volunteers will first be tested with the VR headset B, and during the next visit – with the VR headset A.

Visits

The study includes two visits:

Visit 1 (Day 1): verification of inclusion/non-inclusion criteria, randomization, and testing.

Visit 2 (Day 2): verification of exclusion criteria, testing.

The minimum interval between the two visits is 24 hours and nocturnal sleep is mandatory. The next visit should take place at the same time, taking into account the circadian rhythms. The overall

duration of the study for each volunteer is 2 days (+7 days), if necessary, Visit 2 may be postponed for a maximum period of 7 days.

Stages of each visit are described in details in Section 6.1.

Layout 1. General study layout

Group 1

Headset A, Visit 1

Stage 1	Stage 2	Stage 3	Stage 4
---------	---------	---------	---------

Headset B, Visit 2

Stage 1	Stage 2	Stage 3	Stage 4
---------	---------	---------	---------

Group 2

Headset B, Visit 1

Stage 1	Stage 2	Stage 3	Stage 4
---------	---------	---------	---------

Headset A, Visit 2

Stage 1	Stage 2	Stage 4	Stage 4
---------	---------	---------	---------

4.3. Description of randomization and blinding

In order to observe the “blindness”, the study group of each volunteer will be determined in accordance with their randomization group.

The blind study suggests volunteers’ lack of information about used VR technology. VR headsets will be labelled as A and B, and the volunteer will not be aware of the corresponding technology. Unblinding will take place upon completion of the study.

With a view to a more even distribution of the volunteers, a block randomization design (fixed-length blocks of 10 volunteers balanced by groups) will be used.

Randomization is carried out only after the signing of the Informed Consent Forms and verification of the volunteers’ compliance with all inclusion/non-inclusion criteria (the volunteers are assigned with randomization numbers).

In practice, the implementation of the developed randomization scheme will be carried out using numbered envelopes provided by the Sponsor to the site. Each envelope will contain 10 randomization cards. The investigator will open an envelope and randomly take out randomization cards, which will say “Group 1” or “Group 2”, according to which the volunteers will take part in the study.

The next envelope will be opened as the investigator runs out of randomization cards in the previous envelope in ascending order of the numbers on envelopes.

The distribution by groups is given in Table 2.

Table 2. Distribution of healthy volunteers

	Group 1	Group 2
Number of volunteers	50 healthy volunteers	50 healthy volunteers

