2.5. Characteristics of the study population

The study will include healthy volunteers aged 20 to 60 years, who have applied to the study site. The investigator will suggest taking part in the study to all visitors of the SS, who turned to the SS for any reason. Information about the study and the invitation to take part in the study will also be published on the Internet.

After signing the Informed Consent Form for participation in the clinical study, an assessment of healthy volunteers' eligibility with the inclusion/non-inclusion criteria will be carried out.

Approximately 100 randomized healthy volunteers will be enrolled to the study.

2.6. References to publications and othersources of information used for planning and justification of the clinical trial

For planning and justification of this clinical trial, the literary sources specified in the List of Regulatory Documents and References section were used.

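### Section 4.3 has the investigator draw sequence cards by hand from an opened envelope holding a whole block of ten, so the next assignment is not concealed and the order within a block cannot be verified

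*Protocol*

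**What the plan says.** Section 4.3 fixes the allocation mechanism in some detail.

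- The scheme uses "fixed-length blocks of 10 volunteers balanced by groups".
- "Each envelope will contain 10 randomization cards", and the sponsor supplies these envelopes numbered.
- "The investigator will open an envelope and randomly take out randomization cards, which will say" Group 1 or Group 2.
- "The next envelope will be opened as the investigator runs out of randomization cards in the previous envelope in ascending order of the numbers" on the envelopes.

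The numbers are thus on the blocks. The cards are described only by the group they name. Nothing is said about a fixed order of cards within an envelope, about cards being sealed or covered, or about a person independent of enrolment who holds them.

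On timing, "Randomization is carried out only after the signing of the Informed Consent Forms and verification of the volunteers" against the eligibility criteria. Sections 4.11 and 4.14 give that eligibility check to the investigator. On blinding, section 4.3 speaks only of the volunteers' "lack of information about used VR technology", while section 9.1 names headset A as the investigational device and B as the comparator.

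Table 2 in section 4.3 plans 50 volunteers in each group. Section 4.8 has the site record each volunteer's ID, randomization date and group, and separately each use of a headset. Section 4.9 leaves the decoding information with the sponsor.

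**The concern.** Concealment means that whoever decides on enrolment can neither know nor influence the next assignment. Here the person who judges eligibility also holds the open envelope with all the cards left in the block. A card can be looked at, picked, or returned and replaced by another, and none of this would leave a trace. Block length and balance are printed in the protocol the investigator works from, so part of each block can be worked out by counting alone.

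What is at stake is the order of the two headsets, since every volunteer is meant to receive both. Four things depend on that order being random:

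- the sequence factor in the section 9.2.3 model, which is a comparison between volunteers;
- the assumption that period effects, such as habituation to the stress test, are alike in the two sequence groups (section 4.13 uses the same number sets for all volunteers, so learning between visits is plausible);
- enrolment decisions that should be made without knowledge of the next sequence;
- any use of single-visit data, because section 5.3 does not replace withdrawn volunteers and such data compare different people.

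**Working it through.** **Inputs.** Block of 10, fixed and balanced (4.3). About 100 randomized (2.5), 50 per group (Table 2). The 5:5 content of each envelope is inferred from the stated balance and Table 2: 100 / 10 = 10 envelopes, and 10 × 5 = 50 per group, which matches Table 2.

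**1. Assignments known with certainty, without seeing a card.** An assignment is certain once one group's cards are used up. A given Group 1 card is in that position if it comes after all five Group 2 cards, which has probability 1/6. Five such cards give 5/6, and the same holds for Group 2:

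5/6 + 5/6 = 10/6 = 1.67 per block, or 16.7 over 10 blocks (about 17 of 100 volunteers).

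The last card of every envelope is always certain.

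**2. Correct guesses when always naming the group with more cards left.** For a block of 2m with m = 5:

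m + 2^(2m−1) / C(2m, m) − 1/2 = 5 + 512/252 − 0.5 = 6.53 of 10,

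or about 65 of 100, against 50 by chance. An exact recursion over the cards remaining gives the same two results, 1.67 and 6.53.

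**3. Room for steering at the first draw from a full envelope.** If an unwanted card is set aside, another drawn, and the first then returned:

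- one replacement: 1 − (5/10)(4/9) = 77.8% chance of the wanted group;
- two replacements: 1 − (5·4·3)/(10·9·8) = 91.7%.

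If each card goes back before the next draw, the figures are 1 − 0.5² = 75% and 1 − 0.5³ = 87.5%. If the cards are looked at, it is 100% while the wanted group lasts.

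**4. What reaches the headset contrast.** Take the within-volunteer difference, Visit 1 minus Visit 2. Let τ be the true A minus B effect, and let π₁ and π₂ be the mean period differences in Groups 1 and 2. Without carryover, Group 1 has mean τ + π₁ and Group 2 has mean −τ + π₂. Half the difference between the groups is

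[(τ + π₁) − (−τ + π₂)] / 2 = τ + (π₁ − π₂)/2.

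Stable differences between volunteers have cancelled. Steering biases the contrast in completers only if it makes π₁ differ from π₂, that is, if the volunteers steered to one order change differently from visit to visit. The documents give no figure for π₁ − π₂, so this bias cannot be sized from them.

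**5. What can be checked afterwards.** The section 4.8 records allow a monitor to check the balance of each block, the match between group and headset, and the run of dates. They do not show which card a given volunteer should have received, because as described the draw itself creates that order.

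**The case against.** The strongest reply is that this is a crossover. Both groups receive both headsets, and section 9.2.3 fits sequence, period and headset with volunteers nested in sequence. Steering can alter only the order. The guessing figures measure predictability and are not a bias in HF. This stands and limits the weight of the point. It does not remove the exposures set out above, though two of them are narrow: the protocol specifies no carryover test beyond the sequence term, and it neither gives a dropout rate nor says how single-visit data would be used.

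A second reply is that the card is drawn only after consent and a recorded eligibility check, and that many criteria are measured (age, heart rate, respiratory rate, STAI score). That narrows discretion without closing it. A card that can be seen or deduced is already known while eligibility is being judged. At least one criterion in section 5.2 rests on the investigator's opinion, and section 5 expects about 160 enrolled for 100 randomized.

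A third reply is that allocation is documented. A reader might infer that it cannot be audited at all, but the documents do not support that. Sections 4.8 and 4.11 require logs of group, date, ID and headset, and section 11 provides for monitoring and audit of them. Only the order within a block is beyond checking.

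A reader might also infer that no allocation list exists. Section 4.3 mentions a developed scheme and randomization numbers, and section 4.9 mentions codes held by the sponsor, so that cannot be stated as fact. What can be said is that a hand draw, as described, does not follow any preset order within the envelope.

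Finally, predictability by counting applies to any known fixed block of ten, however well sealed, and fixed blocks are a legitimate choice. That stands, so varying the block size is kept apart from the main change.

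**Conclusion.** The point holds in a limited form. Followed as written, section 4.3 leaves the sequence unconcealed and open to steering by the person who judges eligibility, and individual assignments within a block cannot be verified. By counting alone, about 6.5 of 10 assignments can be guessed and about 1.7 of 10 are certain. These figures assume 5:5 envelopes, a site that knows the block length, and a site that keeps count. The protocol prints the length, and the 5:5 content is inferred.

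The tempting stronger conclusion, that the headset comparison itself is compromised, does not follow. In volunteers who complete both visits the period-adjusted contrast is affected only through a difference in period effects between the sequence groups, for which the documents give no evidence and no size. Nor do the documents show that any card would in fact be looked at or exchanged; the fault is that the procedure does not prevent it. The sample size of 36 in section 9.1 does not depend on this point. The change is worth making because it is cheap and lets the claim of randomization be verified.

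**What to change.** Rewrite the envelope procedure in section 4.3. The sponsor or CRO generates the complete ordered list before enrolment and keeps it. The site receives one sealed, opaque, sequentially numbered envelope per volunteer, each with a single card. Envelopes are opened strictly in number order, only after eligibility has been signed, with the volunteer ID and date written on the envelope. Opened envelopes are kept, so that a monitor can compare each one with the list.

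Cost: about 100 envelopes instead of 10, the list, and a few lines of protocol text. No extra staff, visits or volunteers are needed.

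This closes the steering route and makes each assignment verifiable. It does not change the counting figures while the block of ten stays fixed and known. As an option, use varying block sizes that are not disclosed to the site. The price is a slight possible imbalance between the groups if enrolment stops in the middle of a block.

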4.4. Information about the VR headset

The study will use two identical BoboVR X1 virtual reality headsets. Pure Purr software will be installed on one of the headsets, and another headset will run the sham software. Each of the VR headsets will have the following labelling:

- A or B marking;
- clinical trial protocol code (PurePurr-001).

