4.8. Accounting procedures for virtual reality headsets and volunteers

Storage of virtual reality headsets

Virtual reality headsets should be stored in original packaging, in a safe, dry place, in a closed room or a closet, accessed only by the responsible Investigator and authorized persons.

Terms of distribution, accounting and return of virtual reality headsets

For the purposes of the study, the HCF will receive 2BoboVR X1 virtual reality headsets with pre-installed software (sham and Pure Purr). Each virtual reality headset will be labelled as A or B.

Having received the virtual reality headsets, the responsible Investigator provides signing of the Note of Delivery to the Study Site (2 copies) by the administration of the HCF. All received virtual reality headsets should be registered on the off-balance sheet of the HCF.

Under no circumstances can the investigator allow the use of virtual reality headsets for any purposes other than that specified in the Clinical Study Protocol. The virtual reality headsets should be delivered to the SS in intact packaging.

Upon completion of the study the virtual reality headsets are returned to the Sponsor, as evidenced by the Note of Return from the Study Site (2 copies).

The Investigator conducting the study should keep the Virtual Reality Headset Use Form, stating the following

- 1) Date, time and duration of use of the virtual reality headset
- 2) Type of headset, A or B
- 3) Volunteer's ID

The virtual reality headset will be used by the volunteers in accordance with the regimen corresponding to the study group

Record form for enrolled/screened/randomized volunteers

Volunteers who have signed the Informed Consent Form are registered in the Record Form for Enrolled/Screened/Randomized Volunteers, which states:

- 1) Volunteer's full name
- 2) Volunteer's ID (five digits)
- 3) Date of signing of the Informed Consent Form
- 4) Did the volunteer pass the screening (yes/no)?

- 5) Did the volunteer pass the randomization (yes/no)?
- 6) Date of randomization
- 7) The group to which the volunteer was assigned (1 or 2)
- 8) In case of volunteer's non-compliance based on the results of the screening or his/her exclusion, the reason should be specified in the Volunteer Exclusion column

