In case of AR/ADE, the investigator should take medical measures and actions aimed at their reversal. In the event of the occurrence of AR/ADE health-threatening and/or life-threatening for the volunteer, the investigator is allowed to unblind the randomization code making a telephone call to the study monitor or to another employee of the Sponsor or the CRO ([contact]). The reason for disclosure of the code should be described in detail in the CRF.

All volunteers, who had registered AR/ADE during the study period, should be monitored until their resolution or achievement of clinical stability.

Observation of the volunteers who have suffered from AR/ADE, should continue until complete recovery or determination of the causes of its occurrence. All attempts to obtain additional information should be documented.

The investigator is responsible for all the therapeutic measures and final procedures.

Reporting about AR/ADE

All cases of AR/ADE observed by the investigator or spontaneously reported by the volunteers during the study, including events not directly related to the virtual reality technology, should be recorded in the appropriate section of the CRF.

The Investigator should provide full description of AR/ADE, the degree of severity, the date and time of the beginning and end of the event, the pharmacotherapy, study outcomes, describe the measures for the elimination of AR/ADE, and their consequences. In addition, these data should be provided in the final Clinical Study Report.

The investigator should notify the Sponsor of the study of all RE/ADE with respect to the confidentiality of data: in the primary and subsequent messages, the volunteers are identified by their identification (randomization) numbers, initials and date of birth.

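### Each arm is one physical headset under one fixed letter, so A minus B includes any unit difference and a single code break decodes all 200 sessions

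*Protocol*

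**What the plan says.** All of this is in the protocol.

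- **Hardware (4.4, 4.8).** "The study will use two identical BoboVR X1 virtual reality headsets". Of these, "Pure Purr software will be installed on one of the headsets, and another headset will run the sham software". The software arrives loaded: "the HCF will receive 2BoboVR X1 virtual reality headsets with pre-installed software (sham and Pure Purr".
- **Labels (4.8).** "Each virtual reality headset will be labelled as A or B". For how long: "Upon completion of the study the virtual reality headsets are returned to the Sponsor". Nothing provides for spare units, exchange of software, relabelling, or more than one code per arm.
- **Who knows the letter (4.2, 4.3, 4.8).** The investigator draws a card naming Group 1 or Group 2, each group has a fixed order of A and B, and the use form records for every session "Type of headset, A or B".
- **Analysis (9.2.3).** The mixed model has sequence, period, headset and subject. The treatment contrast is headset A against headset B, with B as reference.
- **Code (4.9, 8, 9.1).** The sponsor keeps the codes confidential until it has received the statistical results. For a health-threatening or life-threatening event, "the investigator is allowed to unblind the randomization code making a telephone call to the study monitor" or to another sponsor or CRO employee. Section 9.1, in defining the superiority limit, identifies headset A as the investigational device and B as the comparator.

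**The concern.** There are two separate consequences.

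**Attribution.** Section 2.1 describes the sham as a similar sequence on the same headset model; the key difference is the missing binaural modification and the missing synchronisation with breathing and heart rate. The cross-over removes differences between volunteers, but not a difference between the two units, because the content travels with the unit in every session. Section 4.5 requires a properly calibrated ECG recorder, the same one for everyone. No comparable check of sound or picture output is stated for the headsets.

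**Blinding.** With one letter per arm, the code cannot be broken for one volunteer alone. The investigator knows the group and the letter for everyone. By section 4.13 the investigator or an assistant also delivers the stress task and announces wrong answers, and by section 4.1 the investigator rates tolerability. Sections 4.9 and 8 make sense only if the investigator is meant not to know which letter is active.

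**Working it through.** **1. The plan's own figure.** Section 9.1 gives n = (1.96 + 1.64)² × 0.35² / (2 × (0.25 − 0.10)²) = 12.96 × 0.1225 / 0.045 = 35.28, rounded up to 36. It reproduces. The point here does not depend on it and does not change it.

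**2. Aliasing.** Let τ be the content effect and u the additive effect of the active-software unit relative to the other. Each volunteer contributes one A and one B session, so, apart from period, the expected A − B is τ + u for all 100 volunteers. As a check, take a design matrix over 200 sessions with columns for content, unit, period and 100 subjects, 103 in all:

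| Assignment | Rank | Columns |
|---|---|---|
| One version per unit throughout (4.4, 4.8) | 102 | 103 |
| Versions exchanged between units for half the volunteers (illustration) | 103 | 103 |

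In the first row content and unit are the same column, and no later analysis can separate them. In the second row half the volunteers estimate τ + u and half τ − u. The average of the two is τ and half their difference is u. If instead a volunteer uses the same unit at both visits, u drops out of the within-volunteer difference, which estimates τ directly.

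**3. What a unit difference could do (assumed range).** The protocol gives no value for u, so the following only illustrates. Assume τ = 0, 100 volunteers and a two-sided 5% test of A − B = 0. If 0.35 is the SD of the within-volunteer difference, SE = 0.35/√100 = 0.035. If it is a per-session SD, SE = 0.35 × √(2/100) = 0.0495. The normal-approximation rejection rate is 1 − Φ(1.96 − u/SE) + Φ(−1.96 − u/SE).

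| Assumed u (relative HF change) | SE 0.035 | SE 0.0495 |
|---|---|---|
| 0 | 5.0% | 5.0% |
| 0.02 | 8.8% | 6.9% |
| 0.05 | 29.8% | 17.3% |
| 0.10 | 81.5% | 52.4% |

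These rates apply to a test against zero. Section 9.1 states the null as a difference of at most 0.10. Against that null, a unit effect of up to 0.10 with no content effect would not push rejection above the nominal level. Sections 7.1 and 9.2.3 read more like a test against zero, so the protocol leaves open which null applies.

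**4. Reach of one disclosure.** 100 volunteers × 2 visits = 200 sessions under one key, 100 on A and 100 on B. With codes that differ by randomisation block of 10, one disclosure would cover at most 10 volunteers, or 20 sessions.

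**The case against.** The best defence is that the two headsets are the same model and are called identical, that each is used once by every volunteer so wear is nearly equal, and that section 2.1 defines the technology as headset plus software, so comparing headset A with headset B is the stated hypothesis. Much of this stands. No unit difference is documented, and it may be negligible. But sameness of model is not a check of delivered sound and picture, and the two arms are defined by what the software plays, not by which unit plays it.

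On blinding, the trigger is remote: two 5-minute exposures in healthy volunteers, with section 2.2 calling the risk of serious reactions insignificant. Section 4.3 also describes the blind in terms of what volunteers know. Both stand as limits on the size of the problem. They do not dispose of it, because sections 4.9 and 8 also withhold the code from the investigator, and section 9.1 prints the key without any emergency.

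Three stronger readings are tempting but unsupported:

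- A reader might infer that the headsets do differ and that the result is biased. Nothing in the protocol shows a difference, and the rejection rates above are not predictions.
- A reader might infer that one code break ends the blind for everyone, STAI included. The call informs the investigator, the STAI is completed by the volunteer, the primary variable is derived from the ECG, and no section passes the code to volunteers.
- A reader might infer that volunteers could break the code by comparing impressions. Each already experiences both headsets, and impressions do not reveal which is active.

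**Conclusion.** The point holds as a design weakness that is cheap to remove, not as evidence of bias. The aliasing is exact: one unit per arm in 200 of 200 planned sessions, so A − B is content plus unit. Its size is unknown. That the assignment is fixed for the whole trial is inferred from pre-installed software, single labels and return at study end; no section contradicts it.

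The blinding weakness is also real but bounded. One code break decodes all 200 sessions for the investigator, exposing the conduct of the stress task and the tolerability rating. Volunteers and their STAI are exposed only if they are told. The key printed in section 9.1 conflicts with section 4.9 and is the more immediate leak, since an investigator working from the protocol can read it. Because the information needed to separate unit from content is never collected, this has to be settled in the design and cannot be left to a later analysis plan.

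**What to change.** - **4.4 and 4.8:** load both versions on both headsets under neutral file codes whose meaning only the sponsor holds.
- **4.3:** have each randomisation card fix the unit and file code for both visits of that volunteer, with codes differing by block of 10.
- **Balance:** either balance version over unit within each sequence, or use the same unit for both visits of a volunteer so that an additive unit difference cancels. A block of 10 has 5 volunteers per sequence, an odd number, so exact balance is reached over pairs of blocks (25 and 25 per sequence over the trial).
- **4.8:** record both unit and file code in the Headset Use Form. With the balanced option, add unit to the model in 9.2.3.
- **9.1:** remove the statement of which headset is investigational, so that it agrees with 4.9.

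Swapping the software and relabelling between blocks looks simpler but is unsafe. About 100 volunteers in 2 months is roughly one block of 10 every 6 days, while Visit 2 may be postponed by up to 7 days, so blocks overlap. A volunteer caught between visits could receive the same content twice. Any swap would have to wait until every volunteer already started has completed Visit 2.

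The emergency unblinding provision stays as it is. The cost is file preparation, new cards and extra fields on the use form, with no new equipment or volunteers and no change in sample size. The downside is a small risk of playing the wrong file, which one version per unit now prevents; the use form allows it to be checked.
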